## **3.0 OBJECTIVES**

### **3.1 Primary Objective and Hypothesis**

The primary objective is to compare the effectiveness of an intensive, 5-session, gender-specific group HIV/AIDS intervention for men, REMAS, to a standard single session HIV/AIDS education group. It is hypothesized that men provided REMAS will engage in fewer risky sexual behaviors as measured by the primary outcome measure of the number of unprotected vaginal and anal intercourse acts during the 90 days prior to the 3 and 6 month follow up assessments than will men provided the standard intervention. The time frame over which to measure risk behavior has varied from a few weeks to one year in studies examining sexual risk behavior. A shorter, more recent time frame should increase the reliability of the self report. A longer time frame provides greater opportunity for risk behavior to occur. This latter issue is especially important in populations such as drug abusers where frequency of sexual behavior varies greatly across and within individuals. The choice of a 90 day time frame provides a balance between these two issues. In addition 90 days was the time frame used in Project Light from which much of the intervention material is derived. It is also hypothesized that being non-monogamous in the prior six months and years of stimulant use will be associated with the frequency of unprotected vaginal and anal intercourse and intervention condition. Specifically, the intervention will be more effective with stimulant users and those with multiple sexual partners. These two variables will be entered into the data analytic model described more fully in section 11.2.

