where  $\varepsilon_k = (\varepsilon_{11k}, \dots, \varepsilon_{I(2m)k})'$  has a multivariate normal distribution with mean zero and covariance matrix  $\sigma^2 R$ . Here the correlation matrix  $R$  contains 1 for its diagonal entries and  $\rho$  for off-diagonal entries. Here  $\sigma^2$  is the variance of  $\varepsilon_{ijk}$  and  $\rho$  represents the correlation between any two observations from the same cohort as well as the correlation between two observations from different cohorts within the same CTP site. Note that we assume that the correlation between two observations from the same cohort is the same as the one between two observations from different cohorts within the same CTP site. Under this linear model, to detect the effect size  $\Delta$  in the average number of unprotected vaginal and anal intercourse between the intervention and control conditions at the type I error  $\alpha$  with a power of  $1-\beta$ , we need the following number of cohorts per condition in the study:

$$m = 2(z_{1-\alpha/2} + z_{1-\beta})^2 \{1 + (I-1) * \rho\} / (I * (\Delta)^2),$$

where  $z_{1-\beta}$  is the  $(1-\beta)$ th percentile of the standard normal distribution. This formula is the same as Formula (5.1) in Donner and Klar (2000).

From the above formula, we see that to calculate a required sample size we need to determine the standardized effect size  $\Delta$ . We have estimated the effect size on the basis of clinically important intervention effects observed in prior studies. The NIMH Multisite HIV Prevention Trial Group (1998) used the number of unprotected vaginal and anal intercourse acts as a primary outcome measure in Project Light. They observed an effect size ( $\Delta$ ) of 0.29. Assuming that we have an intracluster correlation no greater than  $\rho$  of 0.01 and an average of 8 participants per cohort ( $I=8$ ), using the above formula we find that the number of cohorts per condition required to detect the effect size of 0.29 with a type I error rate of 0.05 and a power of 80% is:

$$m = 2 * (1.96 + 0.84)^2 * \{1 + (8-1) * 0.01\} / (8 * (0.29)^2) = 25,$$

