#### **11.6 Analysis of Primary Outcome**

The primary objective is to compare the effectiveness of REMAS, an intensive, 5 session, male-specific group HIV/AIDS intervention, to a standard single session HIV/AIDS education group. It is hypothesized that men provided REMAS will engage in fewer risky sexual behaviors as measured by the number of unprotected vaginal and anal intercourse acts than will men provided the standard intervention. It is also hypothesized that being non-monogamous in the prior six months, years of stimulant use, and the baseline frequency of unprotected vaginal and anal intercourse will be associated with the number of unprotected

vaginal and anal intercourse acts at follow up. These three covariates will be entered into the data analytic model described more fully below. All analyses will be performed using an ITT strategy consisting of all randomized participants. Since our data have two levels of the hierarchical structure, we will apply a marginal semi-parametric regression model to analyze the primary outcome.

Hypothesis 1: REMAS will significantly reduce the number of unprotected vaginal and anal intercourse at both at the 3 and 6 month follow-up times in comparison with the standard single HIV/AIDS education session.

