To test this hypothesis, we let  $Y_{ijk}$  be the frequency of unprotected vaginal and anal intercourse of the  $i$ th subject in the  $j$ th cohort of the  $k$ th CTP site measured at the  $t^{\text{th}}$  follow-up time. Let  $z_{1ijk}$  be the treatment assignment indicator for the  $i$ th subject in the  $j$ th cohort of the  $k$ th CTP site. Here  $m$  is the number of cohorts per condition within the CTP site. To adjust for the possible imbalance between conditions on the baseline value, we include the baseline value as a covariate; let  $z_{2ijk}$  be the baseline frequency of unprotected vaginal and anal intercourse of the  $i$ th subject in the  $j$ th cohort of the  $k$ th CTP site. The other two covariates we plan to include in the model are (1)  $z_{3ijk}$ , a binary indicator on whether the  $i$ th subject in the  $j$ th cohort of the  $k$ th CTP site is non-monogamous in the six months prior to the baseline and (2)  $z_{4ijk}$ , years of stimulant use for the  $i$ th subject in the  $j$ th cohort of the  $k$ th CTP site. As noted by Sen (1997), analyzing change from baseline does not remove the baseline imbalance. Hence, we propose to model the absolute frequency at a particular follow-up time and include the baseline frequency value as a covariate in regression.

The following marginal model for outcome of count will be used to test this hypothesis:

$$(1) \quad \log E(Y_{ijk}) = \beta_0 + \beta_1 z_{1ijk} + \beta_2 t + \beta_3 z_{1ijk} * t + \gamma_1 z_{2ijk} + \gamma_2 z_{3ijk} + \gamma_3 z_{4ijk}$$

where  $t=0$  for 3 months post intervention and  $t=1$  for 6 months post-intervention.

Based on the assumed model (1), our main null and alternative hypotheses are governed by the regression parameters  $\beta_1$ ,  $\beta_2$  and  $\beta_3$ . For example,  $\beta_3 \neq 0$  indicates that over time the effects of the two study interventions are different;  $\beta_3=0$  corresponds to no difference in the effectiveness of the interventions over time. If  $\beta_3=0$ , the parameter  $\beta_2$  estimates the rate of change in the outcome measure from 3 to 6 months post-intervention in the two intervention groups, and the parameter  $\beta_1$  estimates the difference between the experimental and control intervention, which is the same at the two follow-up assessment times.

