### 11.8 Secondary Analyses on compliance on the outcome effects

We anticipate that not all participants will attend all five intervention sessions. To assess whether participants who attend more intervention sessions exhibit greater magnitudes of

behavior changes, in addition to the binary treatment indicator (control vs. REMAS) we will create a three-level attendance covariate (attended no sessions, attended one, two, or three sessions, or attended four or more sessions), as done similarly in the NIMH Multisite HIV Prevention Trial Group (1998). We will then include this attendance covariate and its interaction with the treatment indicator to the regression models proposed above to see whether there is a significant intervention by dose (number of sessions attended) interaction for our outcome variables.

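### Section 3.1 hypothesises that REMAS works better in stimulant users and men with multiple partners, but the model as written in section 11.6 does not test this

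*Protocol*

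**What the plan says.** Section 3.1, under the primary objective, first links non-monogamy in the prior six months and years of stimulant use to both the outcome and intervention condition. It then makes the claim specific: "Specifically, the intervention will be more effective with stimulant users and those with multiple sexual partners". On how this is handled it says: "These two variables will be entered into the data analytic model described more fully in section 11.2".

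Section 11.2 states the primary outcome and the direction of the hypotheses. It contains no model and does not mention either variable.

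Section 11.6 contains the model. It introduces non-monogamy, years of stimulant use and the baseline frequency of unprotected acts as variables expected to be associated with the number of acts at follow-up, and continues: "These three covariates will be entered into the data analytic model described more fully below". After defining treatment (z1) and the baseline count (z2), it adds: "The other two covariates we plan to include in the model are" the non-monogamy indicator (z3) and years of stimulant use (z4). It then says "our main null and alternative hypotheses are governed by the regression parameters" β1, β2 and β3.

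The logistic model in section 11.7 has the same terms. Section 11.8 adds one further interaction, for session attendance: "We will then include this attendance covariate and its interaction with the treatment indicator to the regression models proposed above".

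**The concern.** A claim that an intervention is more effective in one kind of participant is a claim about a difference between treatment effects. In a regression model it needs a treatment-by-covariate term. Section 3.1 presents entering the two variables in the model as the way the hypothesis is taken up, but entering them as main effects answers a different question: whether these men report more or fewer unprotected acts, whichever arm they are in.

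At stake is a hypothesis placed under the primary objective that has no matching analysis in this document, and two sections that state it differently. If the interaction terms are chosen only after the data are seen, the result becomes post hoc, although it was meant to be stated in advance.

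**Working it through.** **1. Hypothesis against model.** Model (1), in plain notation, is

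log E(Y) = β0 + β1·z1 + β2·t + β3·z1·t + γ1·z2 + γ2·z3 + γ3·z4,

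with t = 0 at 3 months and t = 1 at 6 months. The log rate ratio of REMAS against control is β1 + β3·t. Neither z3 nor z4 appears in it, so the model fixes the rate ratio to be the same for monogamous and non-monogamous men and for every length of stimulant use. γ2 and γ3 describe prognosis in both arms alike. The only interaction with treatment is time.

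A simulated example shows the consequence (200,000 overdispersed counts, two equal subgroups, true log rate ratios −0.10 and −0.50). The main-effects model returned a single value of −0.31. Adding z1·z3 returned −0.10 for the first subgroup and an interaction of −0.39, close to the true −0.40.

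**2. Other inconsistencies.** Section 3.1 points to section 11.2, but the model is in 11.6. Section 3.1 speaks first of years of stimulant use and then of stimulant users, while z4 is years of use. The form of the modifier is therefore not settled.

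**3. The plan's own sample size.** Inputs from section 11.3: effect size 0.29, intracluster correlation 0.01, cohort size 8, "with a type I error rate of 0.05 and a power of 80% is" the formula

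m = 2(1.96 + 0.84)² × {1 + 7 × 0.01} / (8 × 0.29²) = 24.94, rounded up to 25 cohorts per condition.

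That is 200 men per condition and 400 in total, as stated. The design effect is 1 + 7 × 0.01 = 1.07. This sizes the overall effect only.

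**4. Power if an interaction term is added.** Assumptions not in the protocol: the modifier is binary, a share p of the men is in one subgroup, the arms are equal within subgroups, and the linear approximation of section 11.3 and its design effect carry over. In SD units the variance of the treatment difference is 4 × 1.07/(N·p) in one subgroup and 4 × 1.07/(N·(1 − p)) in the other, so

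SE(interaction) = √[4 × 1.07 / (N·p·(1 − p))], and power ≈ Φ(0.29/SE − 1.96).

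For N = 560 and p = 0.5: SE = √(4.28/140) = 0.175; 0.29/0.175 = 1.66; Φ(−0.30) = 0.38. The other cases follow in the same way. The 504 is 560 × 0.9, using the protocol's 10% attrition.

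| Subgroup share (assumed) | Power, N = 560 | Power, N = 504 | Interaction detectable with 80% power, N = 560 |
|---|---|---|---|
| 50% | 38% | 35% | 0.49 SD |
| 30% | 33% | 30% | 0.53 SD |
| 20% | 26% | 24% | 0.61 SD |

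On the same basis the overall effect of 0.29 SD has 91% power at 560 and 88% at 504. Detecting an interaction of 0.29 SD with 80% power would need about 1,598, 1,903 and 2,497 men for the three shares.

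**The case against.** **The statistical analysis plan may cover it.** Moderator models are often specified there, and a separate plan may exist. That would be a full answer to a bare omission. Here, though, section 3.1 names the protocol's own model as the vehicle, and section 11.6 writes that model out in full without the terms. Where the protocol wants another treatment interaction, it says so (attendance, section 11.8). The conflict lies within this document.

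**The log link lets absolute effects differ between subgroups.** True, but that follows from the link and is no test of the hypothesis.

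**Stronger readings that the protocol does not support:**

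- A reader might infer that the hypothesis cannot be tested in this trial. Both variables are defined and planned as covariates, so adding the terms makes it testable. Only the model as written does not test it.
- A reader might infer that γ2 or γ3 will be reported as evidence of moderation. Nothing says so. Section 11.6 describes the covariates as associated with the outcome and ties its main hypotheses to β1, β2 and β3.
- A reader might halve the drift behind the planned 80% power and arrive at 29% for an interaction as large as the main effect (2.8/2 = 1.4; Φ(1.4 − 1.96) = 0.29). That figure belongs to 400 men and an even split. The protocol plans 560 and gives no split, so a labelled range is the honest statement.

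**What stands of the other side.** The overall REMAS comparison is untouched, so this concerns an additional hypothesis. The power figures are also approximate: they treat the modifier as binary and the errors as linear with equal variance, whereas z4 is years of use and model (1) is log-linear for counts.

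**Conclusion.** The point holds: the analysis is wrong as written for this hypothesis. Section 3.1 claims effect modification, section 11.6 restates it as association, and model (1) has no parameter for a difference in REMAS effect by partner status or stimulant use. The structural conclusion needs no assumptions, since it can be read off the equation.

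The power range of 24-38% rests on the assumed 20-50% share, a binary modifier and an interaction as large as the whole planned effect. A smaller interaction would have less power. The range therefore supports only the qualitative statement that power is low. It does not describe an analysis using years of stimulant use.

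The test of β1 and the sample size stand. This should be corrected before the data are analysed, but it does not threaten the primary result.

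**What to change.** - Keep model (1) for the primary test.
- Add a pre-specified secondary model with z1·z3 and z1·z4. Report the REMAS rate ratio by monogamy status and by stimulant use, with 95% confidence intervals and interaction p-values. Because model (1) already contains treatment by time, state in advance whether these ratios are given at each visit or averaged over visits.
- Make sections 3.1 and 11.6 state the same hypothesis, and say whether the modifier is stimulant use (yes/no) or years of use.
- Correct the pointer in section 3.1 from 11.2 to 11.6.
- State that power for the interactions is low, give the range with its assumptions, and say that a non-significant interaction will not be read as absence of moderation.

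The cost is small: no new data and no change to the sample size. It is slightly more than two model terms. Section 11.6 imputes missing outcomes from donors matched on the propensity to be missing, and if that step ignores arm and the two modifiers, imputed values can dilute the interaction. The secondary analysis should say how the imputation takes them into account.

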### **3.2 Secondary Objectives**

We will also compare the effectiveness of an intensive gender specific HIV/AIDS intervention for men to a standard HIV/AIDS education on several secondary measures of interest. These variables are of interest as they may be precursors to reducing involvement in sexual risk behavior. It is hypothesized that men provided the gender specific intervention will at follow up assessments be more likely to have engaged in “outer course” (sexual activity to the point of orgasm that does not include penetration of body cavities or exchange of body fluids), have fewer sexual partners, be more likely to possess condoms, be more likely to have taken condoms from clinic supplies, express a more positive attitude toward condom use, report less frequent use of drugs in combination with sexual events, and endorse more egalitarian gender role beliefs than will men in the control group.

## **4.0 STUDY DESIGN**

The proposed study will use a randomized clinical trial to assess the relative efficacy of a five-session gender specific intervention, REMAS, as compared to a single HIV/AIDS education session, for current male patients in MMTP or in ODF. Participants will be a minimum of 560 men in MMTP (N = 280) or ODF (N=280) who have engaged in unprotected vaginal or anal intercourse within the past 6 months. Inclusion of men from both MMTP and ODF will ensure heterogeneity among participants in terms of treatment modalities and drugs of abuse. We do not hypothesize there will be a differential impact of the intervention related to treatment modality as Broome et al., 1998 found comparable effects on reducing sexual risk in MMTP and ODF. The schema for the study design is presented in Figure 1. Male clients in

treatment will be invited to complete the screening interview for the study. Individuals meeting the study inclusion criteria, and agreeing to participate will provide written informed consent and be administered the baseline assessment battery. After completing the baseline assessment participants admitted to the study will be placed into an open cohort of participants waiting for randomization. The cohort will close once there are 8 men in the cohort or four weeks has passed since the first subject was placed in the cohort. If less than 3 men are in a cohort after four weeks have passed, the cohort will remain open until a third participant has been found. Once closed the cohort will be randomly assigned to attend either the five-session REMAS intervention or the one session standard educational intervention. Participants who drop out of the study prior to notification of randomization will be replaced since it is assumed dropping out is not related to randomization outcome. The use of a single one-hour HIV/AIDS education session as a comparison is intended to serve as a standard-of-care condition reflecting the current day-to-day practice of most CTPs as captured in the CTN snapshot described in section 1.1.1. The proposed design does not control for possible attention effects that might be present because the gender specific group receives more attention (five vs one session) than the standard HIV/AIDS education group. The protocol development team did consider adding non-HIV related treatment time to the control group, but rejected that concept in favor of the proposed design because it more closely approximates what currently happens in CTPs. A repeated measures battery will be administered at four points: 1) baseline; 2) immediately post intervention; 3) at approximately three months post-skills building intervention, and 4) at approximately six months post-skills building intervention. Follow up data will be deemed to be collected on time if they are collected within fourteen days prior to or thirty days after the scheduled date for 3-month and 6-month follow-ups and within fourteen days after scheduled date for the immediate post-intervention assessment. The primary outcome measure will be the frequency of unprotected vaginal and anal intercourse in the prior 90 days. Secondary outcome measures include; 1) number of sexual partners; 2) frequency of "outer-course;" 3) attitude towards condoms, 4) possessing condoms, 5) having taken condoms from clinic supplies, 6) frequency of combining of sexual behavior with drug use, and 7) beliefs regarding gender roles.

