## Protocol Schema

Figure 1

[figure not shown]

Figure 2: STUDY FLOW CHART

Protocol Number 0018						
Study Activity	Visit 0	Visit 1	Treatment Sessions (1 or 5)	Visit 2	Visit 3	Visit 4
	Day #	Day #	Day #			
Consent for screening assessment	1					
Screening assessment	1					
Obtain written informed consent	1					
Conduct baseline assessment		1-30				
Randomization of cohort			When 3 participants (but no more than 8) are in the cohort			
Attend intervention			Start approx day 8-26, attend over 1-3 weeks.			
Conduct post intervention assessment				21 days after first treatment session		
Conduct 3 mo. Follow up assessment					15 weeks after 1 st session	
Conduct 6 mo. Follow up assessment						27 weeks after 1 st session

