## **2.2. Rationale for Components Included in the Intervention Package**

The development of the intervention package to be used in this protocol, "Real Men are Safe" (REMAS), was guided by the findings noted in the background and rationale sections above. The intervention is more intensive than is normally provided in CTN CTPs (5 sessions vs. 1 session). The intervention is delivered by male therapists to groups of all male clients. In addition to lecture material, there is liberal use of role-plays and peer group discussions. There is nearly an equal focus on information giving and skills building. Sessions 1, 2, 4 and 5 are all adapted from the PL, TOMen, and HIV-ED materials. An outline for the intervention is provided in Table 2. Two sessions per week are provided in the first two weeks. The fifth session is delivered at the beginning of week 3. Post intervention assessment happens immediately following session 5. The two DATAR manuals provide a total of 12 sessions, while PL was seven sessions. The following principles were used for selecting material. All homework and review of homework were dropped. All duplication was dropped. Activities that focused on strengthening a current intimate relationship were dropped (e.g. conflict resolution and sharing feelings). Demonstration of cleaning injection equipment with bleach was dropped. Focus on sexual health was dropped. More technical aspects of HIV disease and focus on current HIV treatments were dropped. In addition a session targeting the interplay between drug use and sexual behavior (#3) was added for this protocol.

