## **6.3 Administration of Study Therapies**

The control condition intervention will be delivered in a single session of approximately 60 minutes (see table 1). The experimental intervention, REMAS will be delivered in five group sessions of approximately 90 minutes each spread out over three consecutive weeks. The intervention will be manual driven (see table 2).

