### **8.3.4. Sexual and sexual risk behavior assessment**

Items were selected or adapted from the SADAR (Sex and Drug Abuse Relationship Interview; Calsyn et al 2000) and the SERBAS (Sexual Risk Behavior Assessment Schedule; Meyer-Bahlburg et al., 1991; Sohler et al., 2000). Behaviors include: 1) absolute frequency of vaginal intercourse and relative frequency of unprotected vaginal intercourse by (main versus casual) partner type; 2) number, gender, and HIV serostatus of partners; 3) relative frequency of drug (including alcohol) use with sex. The number of unprotected vaginal and anal intercourse acts, which serves as the primary outcome measure, will be derived from two items for the previous 90 days included in this instrument. This is the same primary outcome measure being used in CTN Protocol 0019 (Safe Sex for Women). The items from the SERBAS and the SADAR will be administered using the audio computer-assisted self-interviewing (ACASI) method. Metzger et al. (2000) and Gross et al. (2000) have shown respondents to be more self-disclosive regarding participation in high risk behaviors with ACASI compared to in person, face-to-face interviews. This method lessens the impact of possible social desirability distortions on the self reporting of involvement in risk behaviors.

At the post intervention assessment only the items related to the most recent sexual event will be asked since the time frame being covered is since the intervention started, and not the past 90 days as will be the case for baseline and the 3 and 6 month follow up assessments.

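### The 3- and 6-month visits are 84 days apart but each counts the prior 90 days, so the two primary-outcome counts share some days, and early 3-month visits reach back before REMAS session 5

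*Protocol*

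**What the plan says.** All references are to the protocol.

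- **Visit dates.** Figure 2 (Study Flow Chart) sets the 3-month visit at "15 weeks after 1" and the 6-month visit at "27 weeks after 1", in both cases counting from the first session.
- **Windows.** Section 4.0 treats follow-up data as on time if collected "within fourteen days prior to or thirty days after the scheduled date for 3-month and 6-month follow-ups". It sets no minimum interval between the two visits.
- **Outcome period.** Section 3.1 defines the primary outcome as acts "during the 90 days prior to the 3 and 6 month follow up assessments". Section 8.3.4 says that it "will be derived from two items for the previous 90 days included in this instrument".
- **Length of REMAS.** Section 2.2: "The fifth session is delivered at the beginning of week 3". Section 6.3 describes the five sessions as "spread out over three consecutive weeks". The control condition is one session.
- **Use of the two counts.** Hypothesis 1 in section 11.6 claims a reduction at both follow-up times. Model (1) codes 3 months as t=0 and 6 months as t=1, with a time term (β2) and a treatment-by-time term (β3).

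**The concern.** The recall length, the visit spacing and the windows do not fit together. Hypothesis 1 and model (1) treat the two counts as two successive periods. If the recalls overlap, some acts enter both counts, and the change between visits (β2) and the difference in effect between visits (β3) no longer compare separate periods.

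The second mismatch is at the start of follow-up. A control man has received his whole intervention at session 1, whereas a REMAS man has not finished until about two weeks later. A 3-month recall that reaches into those two weeks counts partly treated time in one arm only, which would tend to pull the 3-month difference toward zero.

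Section 8.3.4 omits the 90-day items at the post-intervention visit because the relevant period there starts with the intervention. The same check of recall against calendar was not carried through to the later visits. Section 3.1 justifies 90 days by reliability, opportunity for risk behavior and consistency with Project Light, and does not mention overlap.

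**Working it through.** The protocol gives no figure for spacing or overlap, so there is none to reproduce. Day 0 is session 1.

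**Scheduled dates**
- 3-month visit: 15 × 7 = day 105. 6-month visit: 27 × 7 = day 189.
- Gap: 189 − 105 = 84 days. Overlap = max(0, 90 − gap) = 6 days, or 6/90 = 6.7%.
- With session 5 at about day 14, the 3-month visit falls 105 − 14 = 91 days after it. The first interval accommodates a 90-day recall; the second does not.

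**Extremes allowed by the windows (−14/+30)**
- 3-month window: days 91 to 135. 6-month window: days 175 to 219.
- Smallest gap: 175 − 135 = 40 days, overlap 50 of 90 (55.6%).
- Largest gap: 219 − 91 = 128 days, no overlap.

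**Typical overlap, assuming independent uniform visit dates over the 44-day windows**
- Let D be the 3-month offset minus the 6-month offset within their windows, triangular on (−44, 44). Overlap = max(0, 6 + D).
- P(gap < 90) = 1 − 38²/(2 × 44²) = 0.63 (0.61 if counted in whole days).
- Mean overlap = 6 + 38³/(6 × 44²) = 6 + 4.7 = 10.7 days (10.9 in whole days).
- P(overlap > 30) = 20²/(2 × 44²) = 0.10.

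**Days before the end of REMAS in the 3-month recall**
- Visit on day 91: recall starts on day 1, so 14 − 1 = 13 days precede session 5.
- Visit on day 105: recall starts on day 15, so none.
- Mean under uniform dates: 13²/(2 × 44) = 1.9 of 90 days (2%).
- If the course instead runs to day 21 (three full weeks, section 6.3), the maximum is 20 days, the mean is 20²/(2 × 44) = 4.5 days, and an on-schedule visit includes 6 days.

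**Effect of possible remedies on mean overlap (same assumption)**
- Drop only the early 3-month allowance (visit 3 on days 105–135, visit 4 on days 175–219): [(44³ − 20³)/264 + 150]/30 = 14.7 days. This is worse than now, because 3-month visits move later and 6-month visits do not. (The 150 is the part of the integral from 44 to 50: (50² − 44²)/2 − 22 × 6.)
- Move only the 6-month visit to week 28 (day 196, window 182–226): on-schedule gap 91 days, overlap 0; mean 43³/(6 × 44²) = 6.8 days.
- Do both, without regard to the man's actual 3-month date: (43³ − 13³)/(264 × 30) = 9.8 days.
- Impose a hard 90-day minimum gap with week 28 and a fixed +30 limit: a man seen on day 135 could be seen no earlier than day 225 and no later than day 226, which leaves two dates.

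**The case against.** Much of the case for leaving the plan alone is sound.

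- **The treatment test.** A reader might infer that double counting invalidates the primary comparison. It does not. Shared days add within-person correlation, and the planned GEE on repeated outcomes accommodates that. Section 11.9 names β1 = 0 as the primary null hypothesis. With 3 months coded t=0, β1 is the 3-month effect when the interaction is kept, so pre-completion days do reach it, but as a small dilution.
- **The 50-day extreme.** A reader might infer that 56% of the 6-month result is then really the 3-month effect. In that case (visits on days 135 and 175) it is mainly the 3-month recall that has moved, to days 45–135. The 6-month recall, days 85–175, shares only days 85–105 with the scheduled 3-month period of days 15–105. That is 20 of 90 days (22%), of which 6 are shared on schedule anyway. Both visits must also be at opposite extremes in the same man.
- **Decay.** Saying that overlap understates decay presumes that the effect decays. The supportable statement is that the contrast between visits is blurred.
- **Pre-completion days.** These are few on average, and REMAS men are not untreated in that interval: the control content comes from REMAS sessions 1 and 2, which fall in the first week. The 6-month recall starts no earlier than day 85 for an on-time visit and is untouched.
- **The 90-day recall.** It is a reasoned choice and matches Project Light, the source of the effect size. It need not change.
- **The windows.** They label timeliness. Nothing in the protocol excludes late data, so tightening them would not by itself guarantee separate recalls, and strict limits could cost follow-up in a population that is hard to trace.

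What remains is that the scheduled dates themselves produce an overlap, and that no provision addresses it.

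**Conclusion.** The mismatch is real and modest. The day counts follow directly from the protocol: 6 shared days on schedule, up to 50 within the windows, and up to about 13 days before session 5 in the REMAS arm's 3-month recall. Only some acts are shared, and visits at least 90 days apart share none. The averages (about 11 shared days and about 2 pre-completion days out of 90) rest on uniform, independent visit dates, which the protocol does not state. The pre-completion figures also take session 5 at about day 14; a course ending on day 21 raises the mean to 4.5 days and the maximum to 20.

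The treatment test stands. What suffers is the reading of β2 and β3 as change from 3 to 6 months and of Hypothesis 1 as a claim about two separate periods, together with a slight dilution of the 3-month effect. The on-schedule overlap can be removed almost without cost, so the schedule should be corrected.

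**What to change.** 1. Schedule the 6-month visit at week 28 (day 196), 91 days after the scheduled 3-month visit. This removes the on-schedule overlap and, under uniform dates, lowers the mean from 10.7 to 6.8 days.
2. Where feasible, book the 6-month visit at least 90 days after the man's actual 3-month visit. Make this a scheduling target, not a condition for accepting data, because a hard rule would leave men seen late at 3 months almost no on-time dates.
3. Aim 3-month visits at day 105 or later, but only together with steps 1 and 2, since dropping the early allowance alone increases the overlap.
4. Keep all data in the primary analysis and record actual visit dates. Add a sensitivity analysis restricted to visit pairs at least 90 days apart and to 3-month recalls that start after session 5. Apply the second restriction in both arms by the same day count from session 1, because control men have no session 5. Visit timing is itself a post-randomization variable, so this analysis should support the primary one and not replace it.

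The cost is an amendment to Figure 2 and section 4.0, a 6-month visit about one week later, and slightly less scheduling flexibility. No visits or participants are added.
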